6.4 Treatment blinding

This is a subject, investigator, and sponsor-blinded study. Subjects, investigators and sponsor will remain blinded to study treatment throughout the study, except where indicated below. At database lock, all roles can be unblinded.

The identity of the treatments will be concealed by the use of study drugs that are all identical in packaging, labeling, schedule of administration, appearance, and odor.

Site staff

With the exception of any unblinded site staff identified below, all site staff (including study investigator and study nurse) will be blinded to study treatment throughout the study.

Unblinding a single subject at a site for safety reasons (necessary for subject management) will occur via the process defined in ([Section 6.7](#) (Emergency breaking of assigned treatment code)).

Table 6-4 **Blinding levels**

Role	Time or Event		
	Randomization list generated	Treatment allocation & dosing	Safety event (single subject unblinded)
Subjects/Patients	B	B	UI
Site staff	B	B	UI
Unblinded site staff (see text for details)	B	UI	UI
Drug Supply and Randomization Office	UI	UI	UI
Unblinded sponsor staff (see text for details)	B	UI	UI
Statistician/statistical programmer/data analysts	B	B	UI
Independent committees used for assessing interim results	B	B	UI
All other sponsor staff not identified above	B	B	UI

B Remains blinded

UI Allowed to be unblinded on individual patient level

6.5 Treating the subject

Indacaterol maleate, indacaterol acetate, and placebo will be administered via the Concept1 inhalation device. IP administration will occur at the site by the subject on Day 1 and Day 14 under the guidance and supervision of site staff and will be administered by the subject at the subject's home on study days 2-13 for each treatment period.

Investigational product should be administered approximately between 6:00 a.m. and 10:00 a.m. every day of each treatment period.

On Day 1 and 14 of Treatment period 1, investigational product (and background ICS medication) should be administered between 06:00 a.m. and 10:00 a.m and within \pm 1h of each other. This means that time of dosing between Day 1 and Day 14 should not differ by more than one hour. On Day 1 and Day 14 of Treatment periods 2 and 3, investigational product (and background ICS medication) should be administered within \pm 1h of the time of study medication administration of Day 1 and Day 14 of Treatment period 1 respectively. This will ensure that assessments are done at approximately the same time of the day in each treatment period.

After each dose inhalation, subjects should rinse their mouths with water. Water used for mouth rinsing should be spat out and should not be swallowed.

One Concept1 inhalation device will be provided for each treatment period for a total of 3 devices dispensed for the duration of the study. Subjects should re-use the Concept1 device for 14 sequential doses for each treatment period.

The last dose on Day 14 should be taken at the site. An extra medication kit (in addition to the one dispensed to the subject) will be assigned for the Day 14 dosing, which will not be dispensed to the subject but kept at the site. On Day 14, one capsule should be taken from the kit kept at the site, and the subject should administer the capsule using the same Concept1 device used during Days 1-13. No new device should be provided for the Day 14 dose.

Sponsor qualified medical personnel will be readily available to advise on trial related medical questions or problems.

See the Site Operations Manual for further details.

6.6 Permitted dose adjustments and interruptions of study treatment

Study drug dose adjustments and/or interruptions are not permitted.

6.7 Emergency breaking of assigned treatment code

Emergency code breaks must occur only when it is required to treat the subject safely. Most often, study treatment discontinuation and knowledge of the possible treatment assignments are sufficient to treat a study subject who presents with an emergency condition. Emergency treatment code breaks are performed using IRT. When the investigator contacts the system to break a treatment code for a subject, he/she must provide the requested subject identifying information and confirm the necessity to break the treatment code for the subject. The investigator will then receive details of the investigational drug treatment for the specified subject and a fax or email confirming this information. The system will automatically inform the study monitor for the site and the Study Team that the code has been broken.

It is the investigator's responsibility to ensure that there is a dependable procedure in place to allow access to IRT in case of an emergency. The investigator will need to provide:

- protocol number
- study drug name (if available)
- subject number

In addition, the investigator must provide oral and written information to inform the subject how to contact the investigator's backup in case of emergency when he/she is unavailable to ensure that un-blinding can be performed at any time.

An assessment will be done by the appropriate site personnel and sponsor after an emergency unblinding to assess whether or not study treatment should be discontinued for a given subject.

6.8 Treatment exposure and compliance

For all study drug treatment administered in the clinic, compliance will be adhered to by administration under the guidance and direct supervision of the investigator/designee. The investigator must promote compliance by instructing the subject to take the study treatment exactly as prescribed and by stating that compliance is necessary for the subject's safety and the validity of the study.

For doses administered at the site, after inhalation in each treatment period, the capsule shell will be checked for residual powder. If residual powder is found, the inhalation procedure will be repeated up to a maximum of 3 times provided that total inhalation time does not exceed 2 minutes. The finding will be recorded in the drug administration section of the (e)CRF. Compliance will be assessed by the investigator and/or designee at each visit. This information should be captured in the source document at each visit. All study treatment dispensed and returned must be recorded on the Drug Accountability Log.

Furthermore, compliance with the intake of inhaled corticosteroid and study drug treatment at home will be monitored closely by a review of a patient diary in which all subjects will record administration each day (washout periods). The subject must also be instructed to contact the investigator if he/she is unable to take the study treatment as prescribed at home.

Pharmacokinetic parameters (measures of treatment exposure) will be determined in all subjects on Day 14 of each treatment period during which they were treated with indacaterol acetate and indacaterol maleate, as detailed in [Section 8.7](#) (Pharmacokinetics).

6.9 Recommended treatment of adverse events

Medication used to treat AEs must be recorded on the Concomitant medications/Significant non-drug therapies eCRF.

6.10 Rescue medication

At screening, all patients will be supplied with an inhaled short-acting β_2 -agonist (100 $\mu\text{g}/\text{puff}$ salbutamol or other short-acting β_2 -agonist at matching dose strength) which they will be instructed to use throughout the study as rescue medication. Rescue medication will be procured by the investigative site. Subjects should be instructed to abstain from taking rescue medication within 6 hours of the start of each site visit unless absolutely necessary. If a subject does use their rescue medication within 6 hours of the spirometry assessments on Day 14 in either of the three treatment periods, the spirometry assessments should continue as planned, with the rescue medication usage recorded in the CRF and the data will be excluded from the PD analysis set.

During the study, subjects will record use of rescue medication in a patient diary. Patients should monitor this use carefully and if they use more than ≥ 12 puffs (100 $\mu\text{g}/\text{puff}$) over 24 hours then they should call the site and inform the site personnel. If rescue medication use continues at this level for another 48 hours on two consecutive days then the patient will meet withdrawal criteria ([Section 7.5](#) Study Stopping rules).

Use of rescue medication must be recorded in the patient diary from screening until Day 15 of the Treatment period 3. Concomitant medications and significant non-drug therapies will be collected in the eCRF from screening through completion of the study.

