11.1 Analysis sets

For all analysis sets, subjects will be analyzed according to the study treatment(s) received.

The safety analysis set will include all subjects that received any study drug.

The PK analysis set will include all subjects with at least one available valid (i.e. not flagged for exclusion) PK concentration measurement, who receive any study drug and no major protocol deviations with relevant impact on PK data.

The PD analysis set will include all subjects with available PD parameter data who received any study drug and experienced no major protocol deviations with relevant impact on PD data. Any PD data for the primary endpoint obtained within 6 hours after rescue medication use or within 7 days of systemic corticosteroid will be set to missing.

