11.4.3 Handling of missing values/censoring/discontinuations

Subjects withdrawn for any reasons other than safety and tolerability may be replaced on a case by case basis.

If one of the 23h 15 min and 23h 45 min values are missing (or set to missing) then the remaining non-missing value will be taken as trough FEV₁. If both values are missing, or if the subject withdrew from the study, regardless of the reason for discontinuation, then trough FEV₁ will be regarded as missing.

If any of the values used in the trough FEV₁ are collected within six hours of rescue medication then the individual FEV₁ value will be set to missing and the imputation rules stated above will then be applied.

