6.1.3.1 Model checking procedures

Subjects withdrawn for any reasons other than safety and tolerability may be replaced on a case by case basis.

If one of the 23h 15 min and 23h 45 min values are missing (or set to missing) then the remaining non-missing value will be taken as trough FEV1. If both values are missing, or if the subject withdrew from the study, regardless of the reason for discontinuation, then trough FEV1 will be regarded as missing.

If any of the values used in the trough FEV1 are collected within six hours of rescue medication or 7 days of systemic corticosteroid then the individual FEV1 within 6 hours after rescue medication use or within 7 days of systemic corticosteroid will be set to missing. If rescue medication is taken during the 24 hour spirometry assessments then from the time of the rescue medication intake, all post-time point spirometry assessments will be considered as missing in this treatment period.

Subgroup analysis:

The primary analysis will be performed by subgroup of patients based on their compliance of study medication within the 7 days before the spirometry assessment: if spirometry assessment is done during day 14, then compliance will be calculated between day 8 and day 14 on a total number of 7 doses.

This analysis will be provided per compliance of study medication within the 7 days before spirometry assessment defined as follows:

- <80% Compliance of study medication within the 7 days before spirometry assessment (less than a total number of 5 doses)
- 80-100% Compliance of study medication within the 7 days before spirometry assessment (more or equal a total number of 5 doses)

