6.2.3.1 Model checking procedures

For the FEV1 AUC (0-4hr) if an observation is missing between two non-missing observations, the AUC will be linearly interpolated between the two non-missing values i.e. the subject's profile will be assumed to be linear between the two available values. Multiple occurrences of such missing values (an observation missing between adjacent non-missing observations) will be handled in a similar manner. But in case of missing consecutive assessments, then the patient profile will be excluded from analysis. No imputation will be made if either the first or the last observation is missing and AUC (0-4hr) is calculated from the available part of the profile ignoring the first and last time points.

For all secondary end points, if a patient takes rescue medication within 6h prior to the spirometry assessments and the visit is not rescheduled to the next day then all spirometry assessments data from this visit and the following visits in this treatment period will be set to missing. If rescue medication is taken during the 24 hour spirometry assessments then from the time of the rescue medication intake, all post-time point spirometry assessments will be considered as missing in this treatment period and AUC (0-4hr) will be considered as missing.

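### After rescue use in the 6 h before Day 14 spirometry, the SAP drops from the by-time FEV1 model the same 23 h 15 min and 23 h 45 min readings that the primary analysis keeps, and Protocol 6.10 does not say which data it excludes

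*Protocol*

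**What the plan says.** The event is rescue use in the 6 h before Day 14 spirometry begins. Four places bear on it.

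- **Protocol 6.10** sets both conduct and data handling: spirometry "should continue as planned, with the rescue medication usage recorded in the CRF and the data will be excluded from the PD analysis set". It does not say whether this means single readings, the Day 14 visit, the whole period or the subject.
- **Protocol 11.1** sets to missing "Any PD data for the primary endpoint obtained within 6 hours after rescue medication use". **Protocol 11.4.3** applies this to the trough: if either contributing value is among those that "are collected within six hours of rescue medication then the individual FEV₁ value will be set to missing", the other value, if available, serves as the trough.
- **SAP Section 4 and SAP 6.1.3.1** repeat the 6 h rule for the primary endpoint. SAP Table 4-1 lists one deviation that excludes a subject from the PD analysis, missing informed consent. It has no code for rescue use.
- **SAP 6.2.3.1**, for secondary endpoints only, provides that after rescue in the 6 h before spirometry, if "the visit is not rescheduled to the next day then all spirometry assessments data from this visit and the following visits in this treatment period" are set to missing.

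**The concern.** The trough is the mean of the readings at 23 h 15 min and 23 h 45 min. SAP 6.2.1 lists the same two readings among the spirometry time points, and SAP 6.2.3 analyses them in the repeated-measures FEV1 model. For a period with pre-visit rescue, the primary analysis would treat them as valid and the by-time model as missing. The by-time estimates at the end of the dosing interval would then rest on fewer subject-periods than the primary result, although a reader would expect the two to agree.

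The rescheduling condition adds to this. It makes the SAP deletion look like a fallback, but Protocol 6.10 tells sites to proceed with the visit. The undefined scope of the 6.10 exclusion also leaves an analyst free to read it in more than one way.

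**Working it through.** The plan gives no figure for pre-visit rescue, so there is none to reproduce. The check is one of timing and of setting the rules side by side.

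**Inputs**
- Thirteen readings per period: −45 and −15 min; 5, 15 and 30 min; 1, 2, 3, 4, 8 and 12 h; 23 h 15 min and 23 h 45 min (Protocol 8.5.1, SAP 6.2.1). The detailed schedule table in Protocol 8.1 shows no 3 h row; the count follows the 8.5.1 list.
- Trough is the mean of the last two (Protocol 11.4.1).
- Those two readings fall on Day 15, under visit numbers 103, 203 and 303 (Protocol 8.1).
- Exclusion window: 6 h.

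**Step 1. When pre-visit rescue can occur.** From −0.75 − 6 = −6.75 h to −0.75 h relative to dosing.

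**Step 2. Gap from rescue to the trough readings.**
- Earliest rescue: 23.25 + 6.75 = 30.0 h and 23.75 + 6.75 = 30.5 h.
- Latest rescue: 23.25 + 0.75 = 24.0 h and 23.75 + 0.75 = 24.5 h.

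The gap is 24.0 to 30.5 h against a 6 h window, so the primary rule never removes the trough for this event.

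**Step 3. The rules side by side.**

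| Source | Applies to | Two trough readings |
|---|---|---|
| Protocol 11.1, 11.4.3; SAP Section 4, 6.1.3.1 | Primary endpoint | Kept |
| SAP 6.2.3.1, visit not rescheduled | Secondary spirometry | Missing, with all 13 readings |
| Protocol 6.10 | Not stated | Depends on the reading |

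Because the SAP clause extends to following visits in the period, it reaches the Day 15 visit and so the trough readings, even if the clause's own visit means Day 14 alone.

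**Step 4. What a 6 h reading-level rule would do in the by-time model.** No current document states this rule for secondary endpoints; it is the change proposed below. The window closes between −6.75 + 6 = −0.75 h and −0.75 + 6 = 5.25 h. The 8 h, 12 h, 23 h 15 min and 23 h 45 min readings are therefore always outside it. A reading exactly 6 h after rescue is counted as inside.
- Rescue at −6.75 h removes 1 of 13.
- Rescue at −4 h removes 7 of 13, the 2 h reading being on the boundary.
- Rescue at −1 h removes 9 of 13.

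So 4 to 12 readings stay, against none under SAP 6.2.3.1.

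**Step 5. How many periods.** Forty-two completers give 42 × 3 = 126 subject-periods. If 5 to 10% had pre-visit rescue (an assumption), 0.05 × 126 = 6.3 to 0.10 × 126 = 12.6, so about 6 to 13 periods would supply a primary trough but no by-time reading.

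**The case against.** The strongest reply is that the primary analysis is specified consistently and that SAP 6.2.3.1 is confined to secondary endpoints, so it contradicts nothing in Protocol 11.4.3. If every visit goes ahead, the rescheduling condition is redundant but the outcome is still defined. Deleting the whole profile is also defensible for AUC 0–4 h, peak FEV1 and time to peak, which use readings from 5 min to 4 h that pre-visit rescue can contaminate. All of this stands, and it limits the point. It does not explain why the by-time model should discard readings taken a day after the rescue that the primary analysis accepts.

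A reader might go further and infer that 6.10 costs the trial primary troughs. The documents do not support that. Section 6.10 speaks of Day 14 spirometry, whereas the schedule puts the trough on Day 15. The excluded data are undefined. The two protocol analysis sections and the two SAP sections listed above keep the trough, and Table 4-1 has no rescue code.

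For scale only, suppose the broad reading were applied, with troughs lost at random in a proportion p of periods. Complete salt–placebo pairs are then n = 42(1 − p)², and the SE is 230 × √(2/n) mL (within-subject SD 230 mL and difference 170 mL from Protocol 11.7). Power per test, t-based, is about 92% with no loss and 91%, 89%, 85% and 76% at p = 2%, 5%, 10% and 20%. These rates are assumptions, and the reading behind them is the less likely one.

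A reader might also infer bias against the salts, since rescue could be more frequent on placebo. That is plausible, but the documents give no rates by treatment.

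**Conclusion.** The inconsistency is real and is more than missing detail. If sites follow 6.10, SAP 6.2.3.1 always removes the 23 h 15 min and 23 h 45 min readings from the by-time FEV1 model in periods with pre-visit rescue, while the primary analysis uses them. This follows from the text and the 24.0 to 30.5 h gap and needs no assumption about rates. The number of periods affected, and any effect on power or bias, cannot be derived from the documents.

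The primary analysis is not shown to be compromised. Section 6.10 could be read to remove the trough, contrary to 11.4.3, but the analysis sections and Table 4-1 point to keeping it. The sample size does not depend on this point.

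Rescue taken during the 24 h profile is a separate matter, outside this point. There SAP 6.1.3.1 says that "from the time of the rescue medication intake, all post-time point spirometry assessments will be considered as missing in this treatment period", which differs from Protocol 11.4.3.

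**What to change.** Three text changes, made before unblinding:

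1. **Protocol 6.10.** Replace the closing exclusion clause with a cross-reference to Sections 11.1 and 11.4.3, stating that only readings within 6 h of rescue are set to missing. Those sections govern the primary endpoint, so refer to the SAP for secondary spirometry.
2. **SAP 6.2.3.1.** For the by-time spirometry models, set to missing only readings within 6 h of pre-visit rescue, so that 23 h 15 min and 23 h 45 min match the primary analysis. State separately that AUC 0–4 h, peak FEV1 and time to peak may remain missing for that period. A reading-level rule suits them poorly: it can remove several consecutive early readings, including the first, and leave peak and time to peak resting on the late ones.
3. **Rescheduling.** Reconcile the SAP's condition about moving the visit with the instruction in 6.10 to proceed. Which visit rule is right is for the sponsor and investigators; this review does not choose one.

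The cost is one protocol clause and one SAP sentence, with the rescheduling condition settled in the same edit. No new data are needed, and the by-time model recovers 4 to 12 of the 13 readings in each affected period.

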6.10.1 Salbutamol usage

Rescue medication allowed during the conduct of the study is salbutamol (100 $\mu\text{g}/\text{puff}$) or any other short-acting β_2 -agonist at matching dose strength. Daily use of rescue medication will be recorded in the patient diary and this should be recorded in the rescue medication eCRF from screening until discharge of patients from the site on Day 15 of Treatment period 3.

6.11 Concomitant treatment

The investigator must instruct the subject to notify the study site about any new medications he/she takes after the subject was enrolled into the study.

All prescription medications, over-the-counter drugs and significant non-drug therapies (including physical therapy and blood transfusions) administered or taken within the timeframe defined in the entry criteria prior to the start of the study and during the study, must be recorded on the Concomitant medications/Significant non-drug therapies CRF.

Medication entries should be specific to trade name, the single dose and unit, the frequency and route of administration, the start and discontinuation date and the reason for therapy.

Each concomitant drug must be individually assessed against all exclusion criteria/prohibited medication. If in doubt, the investigator should contact Novartis before randomizing a subject or, if the subject is already enrolled, to determine if the subject should continue participation in the study.

Regular asthma treatment

To be eligible patients must have received inhaled corticosteroids (ICS) at a regimen that has remained stable for at least 4 weeks prior to screening. Patients must continue their individual ICS dosing regimen and it must remain unchanged throughout the study.

The only exception allowed is:

- When, in the medical opinion of the investigator, the patient experiences an asthma exacerbation requiring the use of additional anti-inflammatory therapy. If an exacerbation occurs during the screening epoch, the patient may be re-screened 6 weeks after resolution of the exacerbation. If the patient experiences an asthma exacerbation after randomization that requires the use of additional anti-inflammatory therapy, the patient must be withdrawn from the study and treated as clinically indicated.

In addition, SABA rescue medication supplied to the patient at screening may be used, as needed, for any asthma symptoms that may occur.

The following medications are allowed for the treatment of asthma or allergic conditions during the study if taken regularly every day as part of the patient's treatment regime, and if treatment has been stabilized (stable dose regimen for 4 weeks) prior to screening:

- Topical corticosteroids in recommended doses and dosage regimens will be allowed for the treatment of eczema.
- Antihistamines, inhaled nasal cromolyn, nedocromil, and inhaled nasal corticosteroids

In addition these are allowed concomitant medications:

- Maintenance immunotherapy (desensitization) for allergies is allowed if treatment has been stabilized for at least 3 months prior to screening, and remains unchanged throughout the course of the study.
- Influenza and pneumonia vaccination is acceptable provided it is administered >48 hours prior to the first dose of Treatment period 1. Vaccinations within 48 hours and after are not allowed for this study.

- Selective Serotonin Reuptake Inhibitors at stable dose for at least 30 days prior to screening and during the trial.
- Topical corticosteroids for skin disease at stable dose for at least 30 days prior to screening.
- H1-antagonists except mizolastine or terfenadine at stable dose/regimen for at least 5 days prior to screening.

Adjustments to long acting β_2 -agonist

The use of any long-acting β_2 -agonist must be stopped during the screening epoch in accordance with [Table 5-1](#).

Subjects using long-acting β_2 -agonists and combination medicines containing LABA must be switched to the as-needed use of short acting β_2 -agonist (i.e. salbutamol MDI) with cessation periods prior to lung function testing in accordance with [Table 5-1](#).

The steroid component of any fixed combination (ICS and β_2 -agonist) therapy must be replaced with the equivalent monotherapy ICS plus the as needed use of a short-acting β_2 -agonist that is provided to the patient at screening.

7 Study completion and discontinuation

